1.2 Overview of NPDR

Diabetic retinopathy is the leading cause of new blindness in the US, with a prevalence rate in adults with diabetes of approximately 28.5% (<https://emedicine.medscape.com/article/1225122-overview>). The global impact of DR-related vision complications is expected to rise given the increasing rates of diabetes across the US and other developed countries. As ocular manifestations often precede other systemic complications of diabetes mellitus, eye care specialists play a critical role in the prevention, diagnosis, and management of diabetic eye disease.

There are several stages of DR, ranging from mild nonproliferative disease to severe proliferative disease. While the most common early clinically manifestations of NPDR include formation of microaneurysms and intraretinal hemorrhages, these patients do not present with any symptoms. Progressing in stage, further damage can be observed such as intraretinal microvascular abnormalities, cotton wool spots, increased numbers of hemorrhages, and venous caliber abnormalities. At any stage in the course of the disease, increased vasopermeability results in retinal thickening (edema) and/or exudates that may lead to a loss in central vision. The proliferative diabetic retinopathy (PDR) stage results from closure of arterioles and venules with secondary proliferation of new vessels on the retina, optic disc, or anterior segment. Common complications of DR that puts the patient's vision at risk and requires either urgent medical or surgical intervention include center involved-diabetic macular edema (CI-DME), tractional retinal detachments, epiretinal membranes, and vitreous hemorrhage. The risk of these complications usually increases as the severity of DR increases, although DME can be present at any stage of DR ([Aiello et al. 1994](#)). The link between diabetic ischemia and subsequent proliferation of angiogenic factors including VEGF has been established.

Preventing the conversion to PDR and the associated vision threatening complications has the potential to improve the quality of a patient lives for decades. The ability to minimize sight-threatening diabetic complications in the working-age population could have significant impact on public health.

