4.2 Exclusion Criteria

1. Presence of any active CI-DME in the study eye as determined by the Investigator on clinical examination, or within the central subfield thickness (CST) of the study eye as determined by SD-OCT evaluated by the CRC, with a CST threshold greater than 320 microns.
2. Evidence of retinal neovascularization on clinical examination or wide-field FA.
3. Any evidence or documented history of prior focal or grid laser photocoagulation or any PRP in the study eye in the last 12 months.
4. Any evidence of optic nerve pallor on clinical examination in the study eye as determined by the Investigator.
5. Any evidence of high-risk characteristics typically associated with vision loss in the study eye as determined by the Investigator.
6. Any evidence of new vascularization anywhere (neovascularization of the iris [NVI], neovascularization of the angle [NVA], neovascularization everywhere [NVE], neovascularization of the disc [NVD]) on clinical examination as per the Investigator, or imaging evaluated by the CRC, in the study eye.
7. Any prior systemic anti-VEGF treatment in the past 12 months.
8. Any prior IVT anti-VEGF treatment in the past 12 months.
9. Any documentation of more than 4 prior anti-VEGF IVT injections in the study eye.
10. Any concurrent intraocular condition in the study eye (eg, cataract or glaucoma) that, in the opinion of the Investigator, would either require surgical intervention during the study to prevent or treat visual loss that might result from that condition or affect interpretation of the study results.
11. History of prior vitrectomy surgery in study eye.
12. Historical or active intraocular inflammation (grade trace or above) in the study eye, other than expected findings from routine cataract surgery.
13. History of vitreous hemorrhage in the study eye within 12 weeks prior to the Screening Visit.
14. History of rhegmatogenous retinal detachment or treatment for retinal detachment or macular hole (stage 3 or 4) in the study eye.
15. Aphakia or pseudophakia with the absence of the posterior capsule in the study eye (YAG capsulotomy is permitted).
16. Spherical equivalent of the refractive error in the study eye demonstrating >8 diopters of myopia. For subjects who have undergone prior refractive or cataract surgery in the study eye, preoperative refractive error in the study eye exceeding 8 diopters of myopia.

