6.6.4 Permitted Medication and Procedures

Following the intravitreal injections of either dose of the EYP-1901 insert (2060 µg or 3090 µg) on Day 1, treatment of the fellow eye will be at the discretion of the Investigator. Any fellow eye therapy should be documented in concomitant meds during the study if required.

After Day 1, all subjects, regardless of treatment assignment, may receive approved anti-VEGF supplemental therapy or other standard of care therapy if they have ocular diabetic complications

warranting intervention. All ocular diabetic complications in the study eye will be managed in accordance with each study center's standard of care and must be documented as an AE.

During the study, participants who develop ocular diabetic complications in the study eye requiring anti-VEGF treatment per standard of care may be administered therapy as required. If needed, the study centers will provide their own supply of FDA-approved anti-VEGF therapy and submit the associated costs for reimbursement. The number of anti-VEGF injections received, the name of the product being injected, and the timing of all injections must be recorded in the source documents and eCRF.

Participants who develop ocular diabetic complications requiring PRP or retinal laser standard of care must have the time of laser treatment recorded in the source documents and eCRF.

Participants who develop ocular diabetic complications requiring surgical intervention standard of care (eg, pneumatic retinopexy, cryopexy, scleral buckle) must have the type of intervention and the time of intervention recorded in the source documents and eCRF.

In this case, the Investigator is required to contact the Medical Monitor prior to administering treatment if feasible.

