7.1.1 Ocular Adverse Events

The following ocular events will be considered AEs for the purposes of this study:

- Decrease in BCVA of ≥ 15 letters or ≥ 3 lines from the previous BCVA measurement
- Moderate or severe (Grade 2 or 3) ocular findings compared to the last ocular examination
- Worsening of >2 steps in anterior chamber cell count or vitreous haze compared to the last ocular examination
- Increase in IOP of >10 mmHg at two visits at least 1 week apart or an increase in IOP to >25 mmHg

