**This document is confidential.**

- Percentage of subjects who developed CI-DME in the study eye through Week 24, through Week 36, and through Week 48.

The occurrence of a CI-DME event in the study eye will be identified via examination of centrally read custom algorithm CST data and adverse events. For the CST data at any given time point, if results are available for no more than 2 raters, the average value will be used, and if results are available for three raters, the median value will be used. CI-DME will have occurred when an adverse event occurs which has a mapped preferred term of 'Cystoid macular oedema', 'Diabetic retinal oedema', or 'Macular oedema', for which the temporally closest CST measurement is greater than or equal to 320 microns.

Two additional endpoints will also be summarized.

- Macular edema (Definition 1) will have occurred when an adverse event occurs which has a mapped preferred term of 'Cystoid macular oedema', 'Diabetic retinal oedema', or 'Macular oedema'.
- Macular edema (Definition 2) will have occurred when an adverse event occurs which has a mapped preferred term of 'Cystoid macular oedema', 'Diabetic retinal oedema', or 'Macular oedema', and which has treatment with a concomitant medication with a mapped preferred term of 'aflibercept', 'ranibizumab', 'bevacizumab', or 'faricimab'.

- Percentage of subjects who received anti-VEGF or additional standard of care intervention due to ocular diabetic complications in the study eye through Week 24, through Week 36, and through Week 48.

Anti-VEGF use is identified in reported concomitant medication data as those medications with ATC code 'S01LA'.

Unique mapped concomitant medication and procedure terms and associated information will be reviewed by masked ophthalmology team members to identify those mapped concomitant medication and procedure terms that indicate the use of additional standard of care intervention due to ocular diabetic complications.

- Percentage of subjects who received PRP in the study eye, inclusive of subjects undergoing vitrectomy with endo-laser, through Week 24, through Week 36, and through Week 48.

Unique mapped procedure terms and associated information will be reviewed by masked ophthalmology team members to identify those mapped procedure terms that indicate receipt of PRP.

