#### Time to Event Endpoints

Time (in weeks) to develop any vision threatening complication (PDR/ASNV) in the study eye through a particular time point (Week 24, Week 36, or Week 48) will be computed as the earliest date of a vision threatening complication in the study eye prior to the particular time point minus the date of study drug administration, plus 1 day, divided by 7 days per week. For subjects not experiencing a vision threatening complication in the study eye prior to the particular time point of interest, the subject will be censored at their date of discontinuation from the study (if prior to the time point of interest) or at the time point of interest.

Time (in weeks) to develop a CI-DME in the study eye, macular edema in the study eye per Definition 1, and macular edema in the study eye per Definition 2 will be computed in a similar manner.

This document is confidential.

Each time to event endpoint will be summarized with the number and percentage of subjects who experienced the endpoint, number and percentage of subjects who were censored, and Kaplan-Meier estimates of median and first and third quartiles. The EYP-1901 treatment arms will be compared to the sham IVT group using a log-rank test. A corresponding Kaplan-Meier plot will be prepared for the FAS only.

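### CI-DME and macular edema count only when an adverse event is filed, and retinal thickness has no by-arm summary after baseline

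*SAP*

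**What the plan says.** **Endpoint rule.** SAP 10.2 says CI-DME will be found from centrally read CST and from AEs. The operative sentence joins the two: "CI-DME will have occurred when an adverse event occurs which has a mapped preferred term of" cystoid macular edema, diabetic retinal edema or macular edema, "for which the temporally closest CST measurement is greater than or equal to 320 microns". Macular edema Definition 1 is the AE alone. Definition 2 is the AE plus treatment with one of four named anti-VEGF drugs. The time-to-event section computes CI-DME and both macular-edema definitions in the same way, and adds: "The EYP-1901 treatment arms will be compared to the sham IVT group using a log-rank test".

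**AE duties.** Protocol 1.2 says of common complications of retinopathy that vision is at risk and each "requires either urgent medical or surgical intervention include center involved-diabetic macular edema (CI-DME"). Protocol 6.6.4 says ocular diabetic complications in the study eye are managed by each center's "standard of care and must be documented as an AE". Protocol 7.1 defines an AE to include any unfavorable sign and worsening of a pre-existing condition. Protocol 7.1.2 has progressive disease recorded on the AE form. The ocular AE list in Protocol 7.1.1 includes "Moderate or severe (Grade 2 or 3) ocular findings compared to the last ocular examination" but has no OCT or CST item.

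**A related endpoint.** SAP 10.2 also plans "Percentage of subjects who received anti-VEGF or additional standard of care intervention due to ocular diabetic complications in the study eye through Week 24" and through Weeks 36 and 48. That endpoint needs no AE, but it pools all ocular diabetic complications.

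**Thickness outputs.** SD-OCT is scheduled at screening, Day 1 and Weeks 4, 12, 24, 36 and 48 (Protocol Table 5-1). SAP 9.3 tabulates baseline CST. SAP 11.6 sends SD-OCT to listings, and the SAP 20 index has listings for SD-OCT, centrally read CST and macular edema events (16.2.6.3 to 16.2.6.5). The table and figure indexes (SAP 18 and 19) contain no CST output.

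**The concern.** Under this rule a CST value can disqualify an AE but can never create an event. At entry the logic is different: Protocol 4.2, exclusion 1, accepts either an investigator finding or CI-DME "as determined by SD-OCT evaluated by the CRC, with a CST threshold greater than 320 microns". An eye that thickens past the threshold in the central reading, with no AE filed, is therefore absent from every CI-DME and macular-edema table.

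Two secondary objectives are touched (SAP 3.2): reducing the incidence of DME, and determining anatomic effects. DRSS change speaks to the second, but no planned output compares retinal thickness between arms after baseline. A reader who wanted thickness change or unfiled crossings would have to rebuild them from listings for about 60 subjects.

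**Working it through.** **1. What happens to one eye.** Take a study eye with central CST past 320 microns and no AE under the three terms.

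| Output | Rule | Result |
|---|---|---|
| CI-DME | AE and CST at or above 320 | not counted |
| Macular edema, Definition 1 | AE | not counted |
| Macular edema, Definition 2 | AE and anti-VEGF | not counted |
| Time to CI-DME | same rule as CI-DME | censored at the time point or at discontinuation |
| Intervention endpoint | anti-VEGF or other standard-of-care intervention | counted only if treated, and not identifiable as CI-DME |
| CST listing 16.2.6.4 | all centrally read values | visible by subject |

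**2. Which eyes are left.** Protocol 6.6.4, 7.1 and 7.1.2 together cover edema that the investigator recognises. No text ties a CST value to an AE, and the documents do not say whether central readings return to the sites. The remainder is a central crossing that was not judged to be edema or was not filed.

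**3. Size.** The documents give no CI-DME rate and no filing rate, so there is no planned figure to reproduce. The arm size is 20 (Protocol 11.1).

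- One eye: 1/20 = 5 percentage points.
- Two eyes: 4/20 = 20.0% (exact 95% CI 5.7 to 43.7) becomes 2/20 = 10.0% (1.2 to 31.7).
- Chance that at least one CI-DME eye in an arm is missed, for assumed true rate p and assumed filed share s: 1 − (1 − p(1 − s))^20. With p = 10% and s = 90% it is 18%. With p = 30% and s = 50% it is 96%.
- If true rates were 30% on sham and 10% on active, and filing were equal across arms, the 20-point difference would become 15, 10 or 5 points at 75%, 50% or 25% filed.

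The width of these ranges shows that the documents do not fix the size.

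**4. Planned CST summaries.** There are five post-baseline SD-OCT visits and no by-arm CST table at any of them. Some efficacy text in SAP 10 and 10.1 is redacted. However, SAP 11.6 is readable, and the efficacy tables are numbered 14.2.1 to 14.2.18 without a gap.

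**5. Would an OCT-only count be too noisy?** All inputs are assumed: a stable eye, independent normal error with SD 3 to 6 microns per scan, five post-baseline scans, threshold above 320. Let z be the distance from true CST to 320 divided by the SD, p = P(Z > z) and q = 1 − p.

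- Any crossing: 1 − q^5. At true CST 315, p is 0.048 (SD 3) or 0.202 (SD 6), which gives 21.7% or 67.7%. At 310 it is 0.2% or 21.7%.
- Two consecutive crossings: 1 − (q^5 + 5pq^4 + 6p²q³ + p³q²). At 315 this is 0.9% or 13.8%. At 310 it is 0.0% or 0.9%.
- Two consecutive crossings, or any crossing with a minimum rise from baseline, in eyes at or below 320 at baseline (simulation): at 315, 3.6% with SD 3 and a 10-micron rise, or 17.0% with SD 6 and a 20-micron rise.

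The rule proposed below uses the minimum rise only when there is no later OCT. For an eye with all five scans, its false-event rate at 315 therefore lies between 0.9% and 3.6% (SD 3) or between 13.8% and 17.0% (SD 6). With a 20-micron rise, the broader simulated rule gives about 20% (SD 3) to 41% (SD 6) at a true CST of 318. Confirmation removes most noise at 310 but not within a few microns of 320.

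**The case against.** The strongest case is that the AE requirement is a deliberate choice for specificity. A single thickness value past 320 is not necessarily edema, and the noise figures above show how poor a bare threshold would be. The site acquires the OCT itself at each visit, alongside dilated ophthalmoscopy and acuity, and nothing says the investigator cannot see the scan. The AE duties are broad, and the list in Protocol 7.1.1 is not stated to be exhaustive. All of this stands. It is why the AE-based definition should stay and why the gap is limited to unrecognised or unfiled crossings. It does not create a numeric CST trigger, so the gap does not close.

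A second objection is that CST is not an endpoint in Protocol 10 or SAP 5.2. That also stands. A reader might infer that the SAP dropped a promised thickness analysis, because the protocol synopsis plans by-arm statistics for imaging endpoints. That phrase does not name CST, so the documents do not support the inference.

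A reader might also infer that sites need not report CI-DME as an AE, or that under-filing favors EYP-1901. The first is contradicted by Protocol 6.6.4. For the second, the documents give no evidence of unequal filing, and the investigators who make the assessments are masked.

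**Conclusion.** The point holds in a limited form. All three edema definitions need a filed AE, so an unfiled central crossing is a non-event in the percentages and censored in the log-rank comparison. The undercount is unknown; each eye is worth 5 points in a 20-eye arm. Independently of that, no planned output summarises retinal thickness by arm after baseline, although anatomic effect is a secondary objective.

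The weight is minor to low-end should-fix. These are secondary matters, Protocol 11.3.7 describes all analysis as descriptive, the study is not powered, and the listings keep the data. Neither the primary endpoint nor the validity of the trial is affected. The filing shares and scan-error SDs used above are assumptions, not document figures.

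The difference between above 320 at entry and at or above 320 in the endpoint might be read as a conflict of definitions. It matters only for an eye at exactly 320 and is a point of wording.

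**What to change.** 1. **Thickness table.** Add one FAS table of centrally read study-eye CST and change from baseline, by arm and visit, labelled descriptive.
2. **Sensitivity count.** Keep the AE-based CI-DME definition and place one OCT-based count beside it. The event is the first post-baseline centrally read CST past the threshold, in an eye not past it at baseline, regardless of AE. It must be confirmed at the next OCT. If there is no later OCT, it needs a minimum rise from baseline that is written into the SAP and set from the reading center's repeatability. Fix the rule before the Week 36 unmasking, or label it post hoc.
3. **No general intervention route.** Counting a crossing because any diabetic eye intervention followed would bring in treatment for other complications, such as PRP for neovascularization. Leave this route out, or limit it to treatment recorded for macular edema.
4. **Wording.** State one inequality at 320 microns and use it consistently.

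The cost is SAP text and one or two tables from data already scheduled for collection, with no new visits or scans. First confirm that every visit's scan is centrally read, which the documents do not state. The downside is that some subclinical or noise crossings will count, mainly in eyes within a few microns of 320. Setting the two counts side by side shows how many events rest on OCT alone.

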5.1 Measurements and Evaluations by Visit

The schedule of study procedures and assessments by visit is presented in [Table 5–1](#). Starting at Week 4, study visits should be conducted within ± 7 days for all scheduled visits.

Table 5-1: Schedule of Study Procedures and Assessments, Study EYP-1901-204

	Screening	Study Treatment and Follow-Up						
	Days -30 to -5	Day 1	Week 4	Week 12	Week 24	Week 36	Week 48	ET ^a
Time Window (in days)			±7	±7	±7	±7	±7	
Informed Consent	X							
Inclusion/Exclusion Criteria	X	X						
Randomization		X						
Demographics	X							
Vital Signs ^b	X	X	X	X	X	X	X	X
Standard 12-lead ECG	X						X	X
Medical and Medication History	X							
Pre-Injection IOP (bilateral)		X						
Ocular Examination (bilateral) ^c	X	X	X	X	X	X	X	X
Study Drug/Sham Dosing ^d (study eye only)		X						
Post-Injection/Sham injection IOP ^e		X						
ETDRS BCVA (bilateral)	X	X	X	X	X	X	X	X
Color Fundus Photography (bilateral) ^f	X	X	X	X	X	X	X	X
Wide-Field FA (bilateral)	X				X	X	X	X
SD-OCT Assessment (bilateral)	X	X	X	X	X	X	X	X
SD-OCTA Assessment (bilateral) ^g	X				X		X	X
Clinical Laboratory Evaluations ^h	X ⁱ			X	X	X	X	X
Urine Pregnancy Test ^j	X						X	X
Blood sampling for PK ^k		X		X	X	X	X	X
Concomitant Medications	X	X	X	X	X	X	X	X
Adverse Events ^l	X	X	X	X	X	X	X	X

BCVA = best corrected visual acuity; CFP = color fundus photography; DRSS = Diabetic Retinopathy Severity Scale; ECG = electrocardiogram; ETDRS = Early Treatment Diabetic Retinopathy Study; ET = early termination; FA = fluorescein angiography; HbA1c = hemoglobin A1c; IOP = intraocular pressure; PK = pharmacokinetic; SD-OCT = spectral domain – optical coherence tomography; SD-OCTA = spectral-domain – optical coherence tomography angiography

Note. During any unscheduled visit or if posterior inflammation is present in the study eye, CFP, SD-OCT, and wide field FA of the study eye should be collected at a minimum.

(table footnotes on next page)

Footnotes for Table 5-1:

- a. Subjects who terminate the study prior to the Week 48 (end of study) visit should undergo all procedures noted for the early termination visit.
- b. Vital signs will include pulse rate, respiratory rate, body temperature, and systolic and diastolic blood pressure (average of 3 readings will be taken in a resting state).
- c. Anterior and posterior segments ocular examination, including dilated ophthalmoscopy, IOP, and slit lamp biomicroscopy (see [Appendix 2](#)).

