## 4. Study Details/Design

### 4.1. Brief Description

[figure not shown]
This is a prospective, randomized, double-masked, multicenter study evaluating the ocular efficacy and safety of 2 different doses of the EYP-1901 IVT insert compared to sham in adult subjects with NPDR. Approximately 60 subjects will be randomized in a 1:1:1 ratio to each of three treatment arms (2060 µg EYP-1901, 3090 µg EYP-1901, or sham IVT injection) across approximately 30 sites in the United States, such that each treatment arm will include approximately 20 subjects.

All subjects, irrespective of treatment arm, will receive an IVT injection on Day 1 in the designated study eye. Subjects in the EYP-1901 treatment arms will receive study treatment which is expected to deliver vorolanib into the vitreous humor for at least 9 months, while subjects in the sham treatment arm will receive a sham injection to maintain masking. Following study drug IVT injection on Day 1, subjects will return at Weeks 4, 12, 24, 36 and 48.

For subjects with unilateral NPDR, the affected eye will be designated as the study eye; for subjects with bilateral NPDR, the study eye will be the more severely affected eye meeting the inclusion/exclusion criteria, ie, the eye having the worse Diabetic Retinopathy Severity Scale (DRSS) score or if equal, the eye clinically judged to be the more severely affected eye as determined by the Investigator. If the eyes are symmetrically affected, the study eye will be the right eye. The fellow eye will receive treatment as needed and according to the Investigator's judgment.

The study design including treatment and visit schedules is shown in [Figure 1](#).

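### SAP 10.2 confirms CI-DME on the single CST scan nearest in time to the adverse event, with no anchor date, direction, maximum gap or treatment limit, so true events can be tested on a scan taken before the edema or after an injection

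*SAP*

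**What the plan says.** SAP 10.2 states that CI-DME events in the study eye are "identified via examination of centrally read custom algorithm CST data and adverse events". The operative rule needs both parts: an AE coded to one of three macular edema preferred terms, "for which the temporally closest CST measurement is greater than or equal to 320 microns". The same event feeds the percentages through Weeks 24, 36 and 48 and the endpoint "Time (in weeks) to develop a CI-DME in the study eye", which is compared with sham by a log-rank test.

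The same section adds two companion endpoints. Definition 1 uses the same AE terms with no CST condition. Definition 2 uses the same terms plus treatment with one of four named anti-VEGF drugs.

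On scan timing, SAP 4.1 says "subjects will return at Weeks 4, 12, 24, 36 and 48", and SD-OCT is scheduled at each of these visits and at Day 1 (Protocol Table 5-1, SAP Table 1). At an unscheduled visit, "CFP, SD-OCT, and wide field FA of the study eye should be collected at a minimum".

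On eligibility, exclusion criterion 1 (Protocol 4.2, repeated in SAP 4.2.2) rules out active CI-DME "as determined by the Investigator on clinical examination, or within the central subfield thickness (CST) of the study eye" on centrally evaluated SD-OCT, "with a CST threshold greater than 320 microns".

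**The concern.** A scan can confirm edema only if it was taken while the edema was present and before treatment reduced it. The nearest scan in time need not satisfy either condition. From Week 12 the scheduled scans are 12 weeks apart. Sites record an onset date for each AE (Protocol 7.1.6), and that date need not be a visit date. Anti-VEGF and other standard-of-care treatment is allowed after Day 1 (Protocol 6.6.4). The confirming scan can therefore come from before the edema began or from after an injection, and a true event then scores as no event.

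Reducing the incidence of DME is a stated secondary objective. With about 20 subjects per arm, one subject scored differently moves an arm's percentage by 1/20 = 5 points and also changes the event count in the log-rank test.

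A smaller point is that the endpoint and the eligibility criterion use different inequalities at the same value, 320 microns.

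**Working it through.** The documents give no CI-DME rate, event count or power figure for this endpoint, so there is no stated figure to reproduce. Three checks can be made.

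**1. What the rule leaves open.** SAP 8.4 gives selection and tie rules for assigning records to visits, but they concern distance from a target study day, not from an AE. SAP 10.2 gives none for this match. SAP 8.3.2 says AE dates will not be imputed, so an AE with a partial start date has no defined nearest scan. The time-to-event text does not say whether the CI-DME event is dated by the AE or by the scan.

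**2. Which scheduled scan is nearest.** Inputs: scans on Day 1 and on the SAP Table 2 target days 28, 84, 168, 252 and 336. Assumptions: the anchor is AE onset, and there is no unscheduled scan. For consecutive scans on days a and b, an onset on day x (a < x < b) matches the earlier scan if x − a < b − x.

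| Interval (days) | Onset days between visits | Nearest scan earlier | Nearest scan later | Tie |
|---|---|---|---|---|
| 1–28 | 26 | 13 | 13 | 0 |
| 28–84 | 55 | 27 | 27 | 1 |
| 84–168 | 83 | 41 | 41 | 1 |
| 168–252 | 83 | 41 | 41 | 1 |
| 252–336 | 83 | 41 | 41 | 1 |
| Total | 330 | 163 (49.4%) | 163 (49.4%) | 4 |

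The nearest scan is 19.0 days away on average and at most 42 days. That maximum becomes (84 + 14)/2 = 49 days if two visits 12 weeks apart each drift by the protocol's 7-day window in opposite directions. It is more than 14 days away for 58% of these onset days and more than 28 days away for 25%.

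Examples:
- Edema is found at Week 24 (Day 168) and its onset is dated Day 120. The distances are 120 − 84 = 36 days to the Week 12 scan and 168 − 120 = 48 days to the Week 24 scan. The Week 12 scan decides, although the Week 24 scan shows the edema.
- Onset is on Days 2 to 14. The nearest scheduled scan is Day 1. An eye still within the eligibility limit on that day could pass only at exactly 320 microns.
- Onset is on Day 140, with an injection before Day 168 and no other scan. Week 24 is nearest (28 days against 56), and that scan is post-injection.

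*Illustration, not from the documents.* Assume 4 true events in an arm of 20 (20%), onset uniform over between-visit days, and every match to an earlier scan falling below 320. If a share f of events has onset away from any scan, the expected loss is 4 × f × 163/330.

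| f | Expected events lost | Expected observed rate |
|---|---|---|
| 10% | 0.2 | 19.0% |
| 25% | 0.5 | 17.5% |
| 50% | 1.0 | 15.1% |
| 100% | 2.0 | 10.1% |

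**3. The two cut-offs.** A CST of 319.5 fails both rules, 320 passes only the endpoint rule, and 320.5 passes both. Every value above the eligibility limit also passes the endpoint limit. Changing the endpoint to above 320 adds no events; it only removes AEs whose matched CST is exactly 320.

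**The case against.** The strongest reply has four parts.

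- **The rule never mentions onset.** An AE has a start and an end. If distance is measured to the whole AE interval, any scan during the AE is at distance zero, and the Week 24 example is judged on the Week 24 scan. This reading is available, but the SAP does not choose it. Nor would it settle which scan counts when several fall within one AE, some before and some after treatment.
- **Same-visit scans limit the problem.** SD-OCT is done at every scheduled visit and should be collected at unscheduled ones, so edema found and dated at a visit normally has a same-day scan. This stands, and it confines the risk mainly to onset dated away from a visit and to missing or unread scans. It is not complete protection. Unscheduled visits need Sponsor approval (Protocol 5.1.2), and the documents do not say that their scans receive the custom-algorithm central read.
- **Definitions 1 and 2 still report these AEs.** This stands for transparency, and Listings 16.2.6.4 and 16.2.6.5 allow an audit. Neither definition tests center involvement, so neither repairs the CI-DME endpoint.
- **The stakes are modest.** This is a secondary endpoint in a study not powered for testing, whose protocol calls all analysis descriptive. That lowers the priority, but a log-rank comparison on this event is still planned.

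A reader might also infer that the cut-off mismatch makes real events go missing. It cannot, because the endpoint rule is the more inclusive of the two.

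**Conclusion.** The point holds as a gap in the event definition. Applied as written, with onset as the anchor, the rule can test a true CI-DME event on a pre-onset or post-injection scan, and so miss it in both the percentages and the time-to-event analysis.

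The 49.4% is a share of between-visit onset days under scheduled scans only. It is not a share of CI-DME events, and it should not be read as half of all events being lost. The loss depends on how often onset is dated away from a scan, which the documents do not give; the 19.0% to 10.1% range rests on the stated assumptions.

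A reader might further infer that treated edema is commoner on sham, so that the sham rate falls and the contrast narrows. The documents give no rate by arm, so that direction is an expectation and not a finding.

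The cut-off difference is a minor consistency point. It lets an eye eligible at exactly 320 microns already meet the CST part of the event at baseline.

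**What to change.** In SAP 10.2:

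- Anchor the match on the AE start date, and state how partial start dates are handled.
- Count CI-DME if any centrally read CST exceeds the cut-off in a window that opens a short stated look-back before AE onset (for example 7 days). The window closes at the first study-eye anti-VEGF, laser or surgical intervention, counting only scans taken before that intervention. If there is none, it closes at AE end or study exit.
- If no scan falls in the window, use the closest pre-intervention scan and flag the event. That scan may predate the edema, so the number of flagged events should be reported.
- State the event date for the time-to-event analysis.
- Use one inequality, above 320 microns, consistent with exclusion criterion 1.
- Keep the current nearest-scan rule as a sensitivity analysis.

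The look-back matters. With a scan of 350 microns on Day 100, an AE dated Day 101 and an injection on Day 103, a window opening at onset could be empty and lose an event that the current rule may count.

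The cost is SAP wording and one extra derivation. Centrally read CST and macular edema events are already planned as Listings 16.2.6.4 and 16.2.6.5, but the sponsor should confirm that unscheduled scans receive the custom-algorithm read. The downside is that the window is longer for untreated than for treated AEs, which gives untreated edema more chances to pass. The SAP should note this.
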